4. OBJECTIVES AND ENDPOINTS

[figure not shown]
Objective	Endpoint
Primary	

 To investigate the safety and tolerability of repeat doses of GSK2982772 in healthy subjects. 	
 Adverse events. Clinical laboratory values (clinical chemistry, haematology and urinalysis). Vital sign measurements (blood pressure, heart rate, respiratory rate and body temperature). Physical examinations. 12-Lead ECG monitoring.
Secondary	

 To characterise the pharmacokinetic (PK) profile of repeat doses of GSK2982772 in healthy subjects. 	
 A 24 hr profile to be collected on Day 1 of Part A and Day 14 of Part B. On Day 1 of Part B, the PK profile will be evaluated following the first dose only. Derived PK parameters for GSK2982772, including area under the plasma drug concentration versus time curve over 24 hr ($AUC_{(0-24)}$) and AUC over each dose interval (i.e. $AUC_{(0-7)}$, $AUC_{(7-14)}$ and $AUC_{(14-24)}$ for TID and $AUC_{(0-12)}$ and $AUC_{(12-24)}$ for BID). Maximum observed plasma drug concentration (C_{max}) following each dose, time to maximum observed plasma drug concentration (T_{max}) following each dose, observed trough plasma drug concentrations (C_0, C_7, C_{14} and C_{24} for TID dosing and C_0, C_{12} and C_{24} for BID dosing).

 To assess the impact of food on the PK of repeat doses of GSK2982772 in healthy subjects at steady state 	
 Derived PK parameters for GSK2982772, including $AUC_{(0-7)}$, $AUC_{(7-14)}$, C_{max}, after 1st dose of day and T_{max} after 1st dose of day.

 To assess potential effect of repeat doses of GSK2982772 on CYP3A4 enzyme activity. 	
 Plasma 4β-hydroxycholesterol to cholesterol ratio pre-treatment and following 14 days of repeat dosing of GSK2982772.
Exploratory	

 To investigate the levels of circulating glucuronide metabolite (M8; GSK3562183) and desmethyl metabolite (M9; GSK2997852) in healthy subjects after single-day and repeat dosing of GSK2982772. 	
 Quantify M8 (GSK3562183) and M9 (GSK2997852) in select plasma PK samples after single-day dosing and at pre-dose and 2 hr following Day 14 of repeat dosing of GSK2982772.

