6.1. Adverse Events Analyses

Adverse events analyses including the analysis of adverse events (AEs), Serious (SAEs) and other significant AEs will be based on GSK Core Data Standards. The details of the planned displays are provided in Appendix 10: List of Data Displays.

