10.10.5. Safety Tables

Safety:	Tables				
No.	Population	IDSL / Example Shell	Title	Programming Notes	Deliverable [Priority]
Part A	(Cohort 1 – sing	gle ascending dos	se, 3-way crossover): Adverse Events (AEs)		
2.1.	Safety (Part A)	AE1	Summary of All Adverse Events by System Organ Class and Preferred Term (Part A)		SAC
2.2.	Safety (Part A)	AE5A	Summary of All Adverse Events by Maximum Intensity by System Organ Class and Preferred Term (Part A)	ICH E3	SAC
2.3.	Safety (Part A)	AE5A	Summary of All Drug-Related Adverse Events by System Organ Class and Preferred Term and Maximum Intensity (Part A)	ICH E3	SAC
2.4.	Safety (Part A)	AE15	Summary of Common (>=10%) Non-serious Adverse Events by System Organ Class and Preferred Term (Number of Subjects and Occurrences) (Part A)	FDAAA, EudraCT	SAC
Part A	(Cohort 1 – sing	gle ascending dos	se, 3-way crossover): Serious and Other Significant Adverse Ev	vents	
2.5.	Safety (Part A)	AE16	Summary of Serious Adverse Events by System Organ Class and Preferred Term (Number of Subjects and Occurrences) (Part A)	FDAAA, EudraCT Only if 3 or more SAEs reported	SAC
2.6.	Safety (Part A)	AE3	Summary of Adverse Events Leading to Permanent Discontinuation of Study Treatment or Withdrawal from Study by Overall Frequency (Part A)	IDSL	SAC
Part A	(Cohort 1 – sing	gle ascending dos	se, 3-way crossover): Laboratory: Chemistry	•	
2.7.	Safety (Part A)	LB1	Summary of Chemistry Changes from Baseline (Part A)	ICH E3	SAC
2.8.	Safety (Part A)	LB17	Summary of Worst Case Chemistry Results by PCI Criteria Post-Baseline Relative to Baseline (Part A)	ICH E3	SAC

Safety	Tables				
No.	Population	IDSL / Example Shell	Title	Programming Notes	Deliverable [Priority]
2.9.	Safety (Part A)	LB17	Summary of Worst Case Lipids Outside Laboratory Normal Range Post-Baseline Relative to Baseline (Part A)		SAC
Part A	(Cohort 1 – sing	gle ascending dos	se, 3-way crossover): Laboratory: Hematology	·	
2.10.	Safety (Part A)	LB1	Summary of Hematology Changes from Baseline (Part A)	ICH E3	SAC
2.11.	Safety (Part A)	LB17	Summary of Worst Case Hematology Results by PCI Criteria Post-Baseline Relative to Baseline (Part A)	ICH E3	SAC
Part A	(Cohort 1 – sing	gle ascending dos	se, 3-way crossover): Laboratory: Urinalysis		
2.12.	Safety (Part A)	UR1	Summary of Worst Case Urinalysis Results (Discrete or Character Values) Post-Baseline Relative to Baseline (Part A)	ICH E3	SAC
Part A	(Cohort 1 – sing	gle ascending dos	se, 3-way crossover): Laboratory: Hepatobiliary (Liver)	·	

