2.13.	Safety (Part A)	LIVER1	Summary of Liver Monitoring/Stopping Event Reporting (Part A)	IDSL	SAC
2.14.	Safety (Part A)	LIVER10	Summary of Hepatobiliary Laboratory Abnormalities (Part A)	IDSL	SAC
Part A	(Cohort 1 – sing	gle ascending dos	se, 3-way crossover): ECG	·	
2.15.	Safety (Part A)	EG1	Summary of ECG Findings (Part A)	IDSL	SAC
2.16.	Safety (Part A)	EG10	Summary of Maximum QTc Values Post-Baseline Relative to Baseline by Category (Part A)	IDSL	SAC
2.17.	Safety (Part A)	EG2	Summary of Change from Baseline in ECG Values by Visit (Part A)	IDSL	SAC

Safety	Tables				
No.	Population	IDSL / Example Shell	Title	Programming Notes	Deliverable [Priority]
2.18.	Safety (Part A)	EG11	Summary of Maximum Increase in QTc Values Post-Baseline Relative to Baseline by Category (Part A)	IDSL	SAC
Part A	(Cohort 1 – sing	gle ascending dos	se, 3-way crossover): Vital Signs	·	·
2.19.	Safety (Part A)	VS1	Summary of Change from Baseline in Vital Signs (Part A)	ICH E3	SAC
Part A	(Cohort 1 – sing	gle ascending dos	se, 3-way crossover): Suicide Risk Monitoring	·	·
2.20.	Safety (Part A)	CSSRS1	Summary of Subjects with C-SSRS Suicidal Ideation or Behaviour during Treatment (Part A)		SAC
Part B	(Cohorts 2, 3, 4	and 5 – repeat do	ose, sequential-group): Adverse Events (AEs))		
2.21.	Safety (Part B)	AE1	Summary of All Adverse Events by System Organ Class and Preferred Term (Part B)	ICH E3	SAC
2.22.	Safety (Part B)	AE3	Summary of Common (>=10%) Adverse Events by Overall Frequency (Part B)	ICH E3	SAC
2.23.	Safety (Part B)	AE5A	Summary of All Drug-Related Adverse Events by System Organ Class and Preferred Term and Maximum Intensity (Part B)	ICH E3	SAC
2.24.	Safety (Part B)	AE15	Summary of Common (>=10%) Non-serious Adverse Events by System Organ Class and Preferred Term (Number of Subject and Occurrences) (Part B)	FDAAA, EudraCT	SAC
Part B	(Cohorts 2, 3, 4	and 5 – repeat do	se, sequential-group): Serious and Other Significant Adverse I	Events	
2.25.	Safety (Part B)	AE16	Summary of Serious Adverse Events by System Organ Class and Preferred Term (Number of Subjects and Occurrences) (Part B)	FDAAA, EudraCT Only if 3 or more SAEs reported	SAC

Safety:	Tables				
No.	Population	IDSL / Example Shell	Title	Programming Notes	Deliverable [Priority]
2.26.	Safety (Part B)	AE3	Summary of Adverse Events Leading to Permanent Discontinuation of Study Treatment or Withdrawal from Study by Overall Frequency (Part B)	IDSL	SAC

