47	All Subjects (Part B)	SP3	Listing of Subjects Excluded from Any Population (Part B)	ICH E3	SAC
Part B (Cohorts 2, 3, 4 and	5 – repeat dose	, sequential-group): Demographic and Baseline Characteristic	S	
48	Safety (Part B)	DM2	Listing of Demographic Characteristics (Part B)	ICH E3 Do not include Weight.	SAC

20518	4
-------	---

ICH: Lis	tings				
No.	Population	IDSL / Example Shell	Title	Programming Notes	Deliverable [Priority]
49	Safety (Part B)	DM9	Listing of Race (Part B)	ICH E3	SAC
Part B (Cohorts 2, 3, 4 and	5 – repeat dose,	sequential-group): Prior and Concomitant Medications		
50	Safety (Part B)	CP_CM3	Listing of Concomitant Medications (Part B)	IDSL	SAC
Part B (Cohorts 2, 3, 4 and	5 – repeat dose,	sequential-group): Exposure and Treatment Compliance	·	·
51	Safety (Part B)	EX3	Listing of Exposure Data (Part B)	ICH E3	SAC
Part B (Cohorts 2, 3, 4 and	5 – repeat dose,	sequential-group): Adverse Events		
52	Safety (Part B)	AE8CP	Listing of All Adverse Events (Part B)	ICH E3	SAC
53	Safety (Part B)	AE7	Listing of Subject Numbers for Individual Adverse Events (Part B)	ICH E3	SAC
54	Safety (Part B)	AE2	Listing of Relationship Between Adverse Event System Organ Classes, Preferred Terms, and Verbatim Text (Part B)	IDSL	SAC
Part B (Cohorts 2, 3, 4 and	5 – repeat dose,	sequential-group): Serious and Other Significant Adverse Ev	ents	
55	Safety (Part B)	AE8CPa	Listing of Serious Adverse Events (Part B)	ICH E3 Include fatal and non-fatal status.	SAC
56	Safety (Part B)	AE14	Listing of Reasons for Considering as a Serious Adverse Event (Part B)	ICH E3	SAC
57	Safety (Part B)	AE8CP	Listing of Adverse Events Leading to Withdrawal from Study / Permanent Discontinuation of Study Treatment (Part B)	ICH E3 Include fatal and non-fatal status.	SAC

ICH: Lis	tings					
No.	Population	IDSL / Example Shell	Title	Programming Notes	Deliverable [Priority]	
Part B (Cohorts 2, 3, 4 and	5 – repeat dose,	sequential-group): Hepatobiliary (Liver)			
58	Safety (Part B)	MH2	Listing of Medical Conditions for Subjects with Liver Stopping Events (Part B)	IDSL	SAC	
59	Safety (Part B)	SU2	isting of Substance Use for Subjects with Liver Stopping Events (Part B)			
Part B (Cohorts 2, 3, 4 and	5 – repeat dose,	sequential-group): All Laboratory			
60	Safety (Part B)	LB5	Listing of All Laboratory Data for Subjects with Any Value of Potential Clinical Importance (Part B)	ICH E3	SAC	
61	Safety (Part B)	LB5	Listing of Laboratory Values of Potential Clinical Importance (Part B)		SAC	

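### Part B (repeat dosing) has no table of all adverse events by intensity; its only intensity table is limited to events judged drug-related

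*SAP*

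**What the plan says.** SAP 6.1 names no individual adverse event table. It says only that "The details of the planned displays are provided in Appendix 10: List of Data Displays", so the list in SAP 10.10.5 is the specification.

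For Part A that list includes Table 2.2, "Summary of All Adverse Events by Maximum Intensity by System Organ Class and Preferred Term (Part A", followed by Table 2.3 for drug-related events by intensity.

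For Part B the adverse event tables are:

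- Table 2.21, "Summary of All Adverse Events by System Organ Class and Preferred Term (Part B"
- Table 2.22, "Summary of Common (>=10%) Adverse Events by Overall Frequency (Part B"
- Table 2.23, "Summary of All Drug-Related Adverse Events by System Organ Class and Preferred Term and Maximum Intensity (Part B"
- Table 2.24, "Summary of Common (>=10%) Non-serious Adverse Events by System Organ Class and Preferred Term (Number of Subject and Occurrences) (Part B"
- Table 2.25, serious events, produced only if three or more are reported
- Table 2.26, events leading to discontinuation of treatment or withdrawal from the study

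SAP 10.10.9 adds Listing 52, "Listing of All Adverse Events (Part B". SAP Table 1, which records departures from the protocol analysis plan, does not mention the difference between the parts.

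The primary objective in Protocol Section 4 is "To investigate the safety and tolerability of repeat doses of GSK2982772 in healthy subjects". Protocol Appendix 4 has the investigator grade every adverse event as mild, moderate or severe, and separately judge its relationship to study treatment.

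**The concern.** The part of the study that gives 14 days of dosing has the less complete severity reporting. A reader of the Part B tables who wants to know how many subjects on each arm had a moderate or severe event can find out only for events judged related.

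That restriction turns on a judgement made after randomisation. Under Protocol Appendix 4 a reasonable possibility of a causal link needs positive facts, evidence or argument; being unable to exclude a link is not enough. An event of uncertain cause can therefore properly be classed as unrelated, and it then drops out of the one Part B table that shows grade. A table of all events by intensity drops no events and does not depend on attribution. Protocol 7.2 allocates Cohorts 3 to 5 in a 9:5 ratio, and the Amendment 02 rationale is a more balanced comparison of active with placebo. That makes an all-event severity summary by arm a natural thing to report.

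**Working it through.** No sample-size or power figure is involved. The check is an inventory of SAP 10.10.5, read by table title and shell code.

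| Content | Part A | Part B | Intensity shown? |
|---|---|---|---|
| All events by class and term | 2.1 (AE1) | 2.21 (AE1) | No |
| All events by maximum intensity | 2.2 (AE5A) | none | Yes |
| Common events by overall frequency | none | 2.22 (AE3) | No |
| Drug-related events by maximum intensity | 2.3 (AE5A) | 2.23 (AE5A) | Yes |
| Common non-serious events | 2.4 (AE15) | 2.24 (AE15) | No |
| Serious events, if three or more | 2.5 (AE16) | 2.25 (AE16) | No |
| Events leading to discontinuation or withdrawal | 2.6 (AE3) | 2.26 (AE3) | No |

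Each part has 6 tables. Those showing intensity number 2 in Part A (2.2 and 2.3) and 1 in Part B (2.23). Tables of all events by intensity number 1 in Part A and 0 in Part B.

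Other places that might fill the gap do not. Figure 2.4 plots common Part B events with relative risk, not grade. Listing 52 covers every Part B event, but it is a subject-level listing without counts by arm. Its layout (shell AE8CP) is not reproduced, so whether it shows intensity cannot be confirmed.

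Tables 2.25 and 2.26 do not stand in for grade either. Protocol Appendix 4 distinguishes severe from serious. A severe event that is non-serious, judged unrelated and does not end treatment would appear in Table 2.21, and in 2.22 or 2.24 if common, always without its grade.

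To show what one such event means at this size, take a cohort with 9 active subjects (Protocol 10.1) and one severe event judged unrelated:

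- Table 2.23 would show 0/9 severe. A table of all events would show 1/9 = 11.1%.
- The exact 95% upper limit is the 0.975 quantile of Beta(x + 1, n − x). For x = 0 this is 1 − 0.025^(1/9) = 33.6%. For x = 1 it is the 0.975 quantile of Beta(2, 8) = 48.2%.
- Both agree with the figures in Protocol 10.1. The difference is 48.2 − 33.6 = 14.6 percentage points.

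The SAP does not plan these limits for its adverse event tables. They only show how much one event weighs in groups this small.

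**The case against.** The case for leaving the plan alone is reasonable. Safety is summarised descriptively and no hypothesis is tested. Protocol 10.4.1 promises no intensity table, so no commitment is broken. All-causality events are already tabulated in 2.21 and 2.22, and serious events and discontinuations are shown whatever their cause. Part B is small enough for Listing 52 to be read by hand. Part B also has a common-event table that Part A lacks, so the difference may be a deliberate choice of display. All of this stands, and it limits the point to one descriptive table. It does not supply the missing counts, and the SAP gives no reason for the difference. Table 2.29 and Listing 62 sit in the Part B blocks but carry a Part A population label. That is compatible with a copying slip but does not prove one.

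A reader might infer more than this. Five stronger readings are not supported:

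- **That the gap affects the halting rules in Protocol 8.1.1.** Every adverse event criterion there already requires a reasonable possibility of relation to study drug. The rules operate during the study, whereas these tables follow database freeze.
- **That a comparison restricted to related events is invalid.** Protocol 7.3 keeps the investigator blinded, so attribution is masked to arm. The restriction loses information; it does not invalidate the comparison.
- **That a large share of events loses its grade.** Neither document indicates what proportion would be judged unrelated.
- **That only Part B bears on the primary objective.** Protocol Section 10 and SAP 2.4 include single as well as repeat doses, so Part A contributes.
- **That tolerability will be concluded from Table 2.23.** Neither document says so. Protocol 10.4.1 rests interpretation on the adverse event displays together with laboratory, vital sign and ECG data.

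**Conclusion.** The point holds in a limited form. Following the SAP as written gives no by-arm summary of intensity for all adverse events in the repeat-dose part, although Part A has one and the grades are collected. The loss is confined to the intensity of Part B events judged unrelated. How many events that is cannot be known from the documents; at up to 9 active subjects per cohort, a single one changes the apparent severe-event count from 0/9 to 1/9. No estimate, analysis population, error rate or dosing decision is affected.

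The conclusion assumes that the titles describe the tables' contents, since the standard shells are not reproduced. The 9-subject denominator is per cohort. SAP 5.1 gives Cohorts 2 and 3 the same 120 mg TID display label, so that column may hold more subjects, which would make the illustration slightly milder for that dose.

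**What to change.** Add one table to the Part B adverse event block of SAP Appendix 10 (10.10.5): the Table 2.2 title with Part B in place of Part A, population Safety (Part B), shell AE5A. Describe Part B severity by arm from that table and keep Table 2.23 as supportive. If the omission was intended, state the reason in the SAP.

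The cost is one line in the display list, any renumbering that follows, and one more run of a shell already used for Tables 2.2, 2.3 and 2.23. No new data are needed, because intensity is already recorded for every event.

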10.10.6. Safety Figures

Safety:	Safety: Figures						
No.	Population	IDSL / Example Shell	Title	Programming Notes	Deliverable [Priority]		
Part A	Cohort 1 – sing	gle ascending dos	e, 3-way crossover): Adverse Events				
2.1.	Safety (Part A)	AE10	Plot of Common (>=10%) Adverse Events and Relative Risk (Part A)	IDSL Common defined as >10%	SAC		
Part A	Cohort 1 – sing	gle ascending dos	e, 3-way crossover): Hepatobiliary (Liver)				
2.2.	Safety (Part A)	LIVER14	Scatter Plot of Maximum vs. Baseline for ALT (Part A)		SAC		
2.3.	Safety (Part A)	LIVER9	Scatter Plot for Maximum ALT vs. Maximum Total Bilirubin (Part A)		SAC		
Part B (Cohorts 2, 3, 4	and 5 – repeat do	se, sequential-group): Adverse Events				
2.4.	Safety (Part B)	AE10	Plot of Common (>=10%) Adverse Events and Relative Risk (Part B)	IDSL Common defined as >10%	SAC		
Part B (Cohorts 2, 3, 4	and 5 – repeat do	se, sequential-group): Hepatobiliary (Liver)				
2.5.	Safety (Part B)	LIVER14	Scatter Plot of Maximum vs. Baseline for ALT (Part B)		SAC		
2.6.	Safety (Part B)	LIVER9	Scatter Plot for Maximum ALT vs. Maximum Total Bilirubin (Part B)		SAC		

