7.2. Method of Treatment Assignment

On Day -1 or Day 1 participants will be assigned a unique number (randomization number) in ascending numerical order. The randomization number encodes the participant's assignment to either GSK2982772 or placebo, according to the randomization schedule generated prior to the study by the Statistics Department at GSK, using validated internal software.

All participants will be centrally randomized using an Interactive Voice/Web Response System (IVRS/IWRS). Before the study is initiated, the telephone number and call-in directions for the IVRS and/or the log in information & directions for the IWRS will be provided to the site.

Study treatment will be dispensed at the study visits summarized in SoA. Each participant will be dispensed blinded study treatment, labelled with his/her unique randomization number, throughout the study. Returned study treatment should not be re-dispensed to the participants

In Cohorts 1 and 2, subjects will be randomized in a 3:1 ratio to either GSK2982772 or placebo. In Cohorts 3, 4 and 5, subjects will be randomized in a 9:5 ratio to either GSK2982772 or placebo. In Cohort 1, the subjects will be randomized to one of four sequences (ABC, ABP, APC, PBC), where the treatments are:

A	120 mg TID
B	240 mg TID
C	360 mg BID
P	Placebo

The planned dose levels are defined in Section 5.1.

The randomization will reflect the fact that at least 2 of the 12 subjects in Cohorts 1 and 2 and at least 2 of the 14 subjects in Cohort 4 and 5 (one subject will receive GSK2928772 and one subject will receive matched-placebo) will be dosed first (on Day 1) in each part to enable dose staggering.

Once a treatment allocation number has been assigned to a subject, it cannot be reassigned to any other subject.

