5. CONSIDERATIONS FOR DATA ANALYSES AND DATA HANDLING CONVENTIONS

5.1.	Study Treatment & Sub-grou	up Display Descriptors

Treatment Group Descriptions											
	RandAll NG	Data Displays for Reporting									
Code	Description	Description	Order in TLF								
Р	Placebo TID Single Dose	Placebo	1								
Q	Placebo BID Single Dose	Placebo	1								
Α	GSK2982772 120 mg TID Single Dose	GSK 120 mg TID	2								
В	GSK2982772 240 mg TID Single Dose	GSK 240 mg TID	3								
С	GSK2982772 360 mg BID Single Dose	GSK 360 mg BID	4								
R	Placebo TID Repeat Dose	Placebo	1								
S	Placebo BID Repeat Dose	Placebo	1								
D	GSK2982772 120 mg TID Repeat Dose	GSK 120 mg TID	2								
E	GSK2982772 240 mg TID Repeat Dose	GSK 240 mg TID	3								
F	GSK2982772 360 mg BID Repeat Dose	GSK 360 mg BID	4								
G	GSK2982772 Cohort 3 Repeat Dose	GSK 120 mg TID	2								
н	GSK2982772 Cohort 4 Repeat Dose	GSK 240 mg TID	3								
J	GSK2982772 Cohort 5 Repeat Dose	GSK XX mg TID/BID ^[1]	3 or 4								
Т	Placebo Cohort 3 Repeat Dose	Placebo	1								
U	Placebo Cohort 4 Repeat Dose	Placebo	1								
V	Placebo Cohort 5 Repeat Dose	Placebo	1								

NOTES:

^[1] Dose level not required as the study met the PK stopping criteria at the end of Cohort 4.

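### The SAP's only between-group measure for adverse events is a relative risk, which has no finite value for events seen only on drug and, in Part A, compares columns that share participants

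*SAP*

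**What the plan says.** SAP 10.10.6 lists two adverse-event figures, both on shell AE10. Figure 2.1 is "Plot of Common (>=10%) Adverse Events and Relative Risk (Part A" and Figure 2.4 is "Plot of Common (>=10%) Adverse Events and Relative Risk (Part B". The programming note to each reads "Common defined as >10" per cent, while both titles say at least 10%. Neither entry names the contrast, a confidence interval or a rule for zero counts.

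SAP 10.10.5 lists the adverse-event tables, starting with Table 2.1, "Summary of All Adverse Events by System Organ Class and Preferred Term (Part A", and Table 2.21, "Summary of All Adverse Events by System Organ Class and Preferred Term (Part B". SAP 5.1 makes placebo a display group of its own, first in order, and pools the placebo codes into it. For example, "Placebo Cohort 3 Repeat Dose" is displayed simply as placebo.

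For Part A, Protocol 7.2 states: "In Cohort 1, the subjects will be randomized to one of four sequences (ABC, ABP, APC, PBC", with A, B and C the three active regimens and P placebo.

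On intensity, Part A has Table 2.2 (all events by maximum intensity, shell AE5A) and Table 2.3 (drug-related events). Part B has only Table 2.23, "Summary of All Drug-Related Adverse Events by System Organ Class and Preferred Term and Maximum Intensity (Part B".

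**The concern.** Adverse events are a primary endpoint. The rationale for Protocol Amendment 02 says that, after arrhythmias led to a dosing hold, allocation in Cohorts 3 to 5 was changed to 9:5 to balance the active-placebo comparison better. The one effect measure chosen for that comparison fails for events seen on drug and never on placebo, which a safety reader most wants to see. At 9 or so per column such patterns are common even when drug and placebo have the same true rate.

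The Part A columns are also not separate groups. They come from a three-period crossover, and SAP 10.4.2 counts an event that worsens in a later period under both periods. An interval built for two independent proportions would not fit those data.

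In the 14-day part, the severity of events would be tabulated only after a causality judgement had filtered them.

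**Working it through.** **The plan's own figures.** The documents give no figure for the relative-risk plots. The nearest are the exact 95% upper limits in Protocol 10.1. For 0/9, 1 − 0.025^(1/9) = 33.6%. For 1/9, the 97.5th percentile of Beta(2, 8) is 48.2%. Both agree with the protocol.

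**Group sizes.**
- Part A has 12 participants on four sequences. The 3:1 ratio implies 3 per sequence (an inference), so each of A, B, C and P is received by 3 × 3 = 9.
- In Part B, 240 mg TID has 9 (Cohort 4). 120 mg TID pools Cohorts 2 and 3 under one label. The number dosed in Cohort 2 is not given, so the range is 1 + 9 = 10 to 9 + 9 = 18.
- Pooled Part B placebo is (1 to 3) + 5 + 5 = 11 to 13. Cohort 5 was not run, per the note in SAP 5.1.

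**Events with no finite ratio.** Let a0 = (1 − p)^(n active) and p0 = (1 − p)^(n placebo), with the same true rate p in both groups and independence. Among events seen at least once:
- drug only (no finite ratio): p0(1 − a0) / (1 − p0·a0)
- placebo only (ratio exactly 0): a0(1 − p0) / (1 − p0·a0)

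Example, 9 v 9 at p = 10%: a0 = p0 = 0.9^9 = 0.387, so 0.387 × 0.613 / (1 − 0.150) = 0.279.

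Each cell shows drug only / placebo only, in %. The rates are assumptions, because the documents give none.

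| Active v placebo | 5% | 10% | 20% |
|---|---|---|---|
| 9 v 9 (Part A) | 38.7 / 38.7 | 27.9 / 27.9 | 11.8 / 11.8 |
| 9 v 11 (240 mg TID) | 32.8 / 42.4 | 21.9 / 30.3 | 7.5 / 12.4 |
| 9 v 13 (240 mg TID) | 28.1 / 45.3 | 17.3 / 32.1 | 4.8 / 12.8 |
| 10 v 11 (120 mg TID) | 34.6 / 39.2 | 23.0 / 26.9 | 7.7 / 9.9 |
| 18 v 13 (120 mg TID) | 38.9 / 24.3 | 22.5 / 11.6 | 5.4 / 1.7 |

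**Sensitivity of the drug-only share.**
- At a 30% rate it falls to 3.9% (9 v 9).
- With a within-participant correlation of 0.5 in Part A it is about 31%, 23% and 10%.
- If 'common' means 10% of the two columns combined, it is 20%, 16% and 8% at 9 v 9, and 4.5%, 3.5% and 1.7% at 9 v 13.
- If 'common' is judged in either column, it is 42%, 21% and 5% at 9 v 13. The 9 v 9 row is unchanged, since one event in 9 is 11.1%.
- Pooling the Part B active doses (19 v 11 to 27 v 13) does not remove it: 44–45%, 24–28% and 5.5–8.5%.

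**What each measure gives.** For 2/9 v 1/9 the ratio is 2.0. The standard error of its log is √(1/2 − 1/9 + 1 − 1/9) = 1.13, giving 0.22 to 18.3. For 2/9 v 0/9 there is no ratio. The risk difference is +22 points. The Wilson limits are 0.063 to 0.547 and 0 to 0.299, so the Newcombe limits are 0.222 − √(0.159² + 0.299²) = −12 points and 0.222 + (0.547 − 0.222) = +55 points.

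**Overlap in Part A.** A and P are both received in ABP and APC, B and P in ABP and PBC, and C and P in APC and PBC. Each pair is 2 × 3 = 6 participants of the 9 in each column.

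**Threshold.** At least 10% and more than 10% differ only where exactly 10% can occur, such as 1/10. The 120 mg TID column has 10 only if a single Cohort 2 active participant is pooled with nine from Cohort 3.

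**The case against.** The study is descriptive and tests no hypotheses. A reader might infer that the plots are the only active-versus-placebo comparison of adverse events. They are not: the tables set placebo beside each dose, and events seen only on drug remain in Tables 2.1 and 2.21 and in the full listings (13 and 52). Relative risk is the only listed effect measure, which is a narrower statement.

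A reader might also infer that the figures will drop or misplot drug-only events, or that the Part A interval is wrong. The documents do not support either. AE10 is not reproduced, so it may hold a zero-count convention and may show no interval. A bare ratio of two observed proportions is still a valid description in a crossover.

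It is tempting to add the placebo-only events and quote 77%, 56% and 24% at 9 v 9. But a ratio of 0 is a defined value and belongs to the opposite pattern, so only the drug-only share counts here.

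Finally, a risk difference at these sizes is also imprecise, and where both measures exist the choice is partly preference. All of this stands. It limits the claim but leaves the SAP without a stated rule for a frequent case, and without a stated method for shared participants.

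**Conclusion.** The point holds in a limited form. Relative risk is the only between-group adverse-event measure the SAP lists. Under equal true rates of 5%, 10% and 20%, it has no finite value for about 39%, 28% and 12% of events seen at least once at 9 v 9, and 28%, 17% and 5% at 9 v 13. These shares rest on assumed rates and independent groups, and they move with how 'common' is applied. A further share have a ratio of 0.

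The Part A overlap of 6 in 9 is exact if there are 3 participants per sequence. It would invalidate an independent-groups interval if one is drawn. The missing Part B table of all events by maximum intensity is a plain asymmetry with Part A and needs no assumption. The threshold mismatch is real but minor.

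These are inexpensive improvements to reporting. No adverse-event data would be lost under the current plan.

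**What to change.** - **Figure 2.4:** plot the risk difference, each active dose minus pooled placebo, with Newcombe or Miettinen-Nurminen 95% intervals. It has a value at every count, so no zero-count rule is needed.
- **Figure 2.1:** show percentages by treatment only, or a within-participant difference for those who received both the dose and placebo. Do not use an independent-groups ratio or interval.
- **Part B tables:** add an AE5A table of all adverse events by maximum intensity, matching Table 2.2.
- **Threshold:** use at least 10% in the title and the note, as in Tables 2.4, 2.22 and 2.24. Because one event in 9 already qualifies, a minimum of two participants per column may look attractive. It would remove every 1/9 v 0/9 event, which is the drug-only pattern the figure should show, so it should not be adopted.

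Cost: two figures leave the sponsor's standard shell, one table is added on an existing shell, and the intervals will be wide, as the 2/9 v 0/9 example shows. Nothing changes in conduct or data collection.
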